#### **Patient Cell Processing**

All cell processing will be conducted in accordance with approved DTM policies and procedures.

***Formulation and Preparation Elutriated Monocyte Placebo Vaccine:*** Autologous elutriated monocyte placebo cell vaccines will be prepared under cGMP conditions from cryopreserved patient monocytes obtained during the original Week 0 apheresis. Autologous monocytes for these placebo vaccines will be enriched from peripheral blood MNC apheresis collections by counter-flow elutriation, aliquoted into at least 8 vials with  $\sim 333 \times 10^6$  cells/vial and cryopreserved for future preparation of the elutriated monocyte placebo cell vaccine products. Elutriated monocytes will be thawed the morning of scheduled vaccine delivery. After thaw, elutriated monocytes will be concentrated down at  $40 \times 10^6$  cells/mL in infusion media (Plasma-Lyte A containing 10% autologous heat inactivated plasma). The final, volume-reduced elutriated monocyte product will be prepared in sterile syringes for fresh administration intradermally. A validated manufacturing process described in the Department of Transfusion Medicine, Clinical Center, NIH standard operating procedures will prepare the elutriated monocyte placebo vaccine product. Detailed standard operating procedures for processing, labeling, storage, and quality assays are available on site in the Cell Processing Section of the Department of Transfusion Medicine.

***Stability and Storage:*** Autologous ME TARP peptide-pulsed dendritic cell vaccines will be harvested from the 5-day culture product and autologous elutriated monocyte placebo vaccine from the single day thaw product. Both will be packaged for fresh administration on the same day according to Standard Operating Procedures of the Department of Transfusion Medicine. A fixed autologous ME TARP peptide-pulsed dendritic cell or elutriated monocyte placebo vaccine dose of  $20 \times 10^6$  viable cells/ in 0.25mL or 0.5mL will be administered immediately upon

receipt in the clinical setting. Post packaging tests indicated that the product is stable for at least 2 hours.

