**Figure 9**

## 3.2 VACCINE ADMINISTRATION

The vaccine manufacturing schema is described in **Appendix C** and manufacturing procedures will follow the NIH Center for Cellular Engineering (CCE) Protocol Specific Instructions (PSI) and Standard Operation Procedure (SOP). All patients will undergo 15-18L apheresis to remove peripheral blood monocytes for dendritic cell preparation as well as peripheral blood mononuclear cells for flow cytometry and immunologic studies at their Week 0 visit. Cells used for subsequent dendritic cell maturation will be derived from monocytes frozen during the initial apheresis. Apheresis may be repeated any time if additional plasma or cell aliquots are needed to manufacture the vaccine. Eligible subjects will receive autologous ME TARP dendritic cell or elutriated monocyte vaccine placebo beginning at Week 3. Each dose can be delivered starting from -1 week of the target date until the maximum delay described in Section **3.3.2**. Patients will be assessed prior to each dose, no earlier than 10 days prior to the administration of the

investigational product. This assessment will include a CBC, acute care panel and liver panel. Refer to [Appendix C](#) for details concerning the cGMP production of peptide-pulsed dendritic cells and elutriated monocyte placebo by the NIH Clinical Center Department of Transfusion.

- Autologous ME TARP DC and elutriated monocyte placebo vaccine preparations will be assessed for release standards (nucleated cell content and concentration, appearance, flow cytometric verification of DC validation markers, viability  $\geq 60\%$ , and product sterility and safety testing) prior to release for vaccine administration to the patient.
- For both groups, the investigational product will be administered intradermally in two sites on the forearm with a maximum volume of 0.5 mL per injection. Administration will be alternated between the left and right forearms with each vaccination, with the exception of patients with a contraindication to using a particular arm. In these instances, consecutive doses in the same arm will be allowed. All patients will receive a total of 6 doses of vaccine ( $20 \times 10^6$  *viable* cells/dose,  $+\/- 10\%$ ) delivered at Weeks 3, 6, 9, 12, 15, and 24 and will undergo scans at Weeks 48 and 96 for restaging.

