#### **ME TARP Peptide-Pulsed Dendritic Cells**

**Background:** Autologous dendritic cells prepared from peripheral blood monocytes will be loaded with the following 7 different TARP-derived peptides:

• WT TARP 27-35	(9 mer, HLA-A*0201 restricted)
• EE TARP 29-37-9V	(9 mer HLA-A*0201 restricted)
• TARP 1-20: MQMFPPSPLFFFLQLLKQSS	(20 mer, HLA non -restricted)
• TARP 11-30: FFLQLLKQSSRRLEHTFVFL	(20 mer, HLA non -restricted)
• TARP 21-40: RRLEHTFVFLRNFSMLLRG	(20 mer, HLA non -restricted)
• TARP 31-50: RNFSMLLRLRGIGKKRRATRF	(20 mer, HLA non -restricted)
• TARP 41-58: IGKKRRATRFWDPRRGTP	(18 mer, HLA non -restricted)

Different fractions of autologous dendritic cells will be pulsed individually with only one of these peptides and the seven fractions will be combined before administration to the patient.

**Formulation and Preparation ME TARP DC Vaccine:** Autologous peptide-pulsed dendritic cell vaccines will be prepared under cGMP conditions from cryopreserved patient monocytes obtained at during the original Week 0 apheresis. Autologous monocytes for dendritic cell culture will be enriched from peripheral blood MNC apheresis collections by counter-flow elutriation, aliquoted into at least 8 vials with  $\sim 333 \times 10^6$  cells/vial and cryopreserved for future preparation of the dendritic cell products. After thaw, the monocytes will be placed into a 5 day culture with rhIL-4 and rhGM-CSF to generate immature dendritic cells, followed by pulse with KLH and maturation with LPS and IFN- $\gamma$ , and pulsed with TARP peptide. After removing peptide-pulsing media, dendritic cells will be concentrated down at  $40 \times 10^6$  cells/mL in infusion media (Plasma-Lyte A containing 10% autologous heat inactivated plasma). The final peptide-

loaded, volume-reduced mature dendritic cell product will be prepared in sterile syringes for fresh administration intradermally. A validated manufacturing process described in the Department of Transfusion Medicine, Clinical Center, NIH standard operating procedures will prepare the dendritic cell vaccine product. Detailed standard operating procedures for processing, labeling, storage, and quality assays are available on site in the Cell Processing Section of the Department of Transfusion Medicine.

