#### 15.4 APPENDIX D: VACCINE BRANCH VACCINE REPORT CARD (VRC)

**Date of Administration (Day 1)** \_\_\_\_\_  
**Investigational Drug Dose #**  1  2  3  4  5  6 [a total of  $20 \times 10^6$  viable cells]

**Total Injection Volume**   $0.5 \times 2 = 1.0$  (ml)

[figure not shown]

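### At the stated 40 million cells/mL, the report card's 1.0 mL holds twice the 20 million viable cells it is labelled with, and Appendix C leaves its volumes undefined

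*Combined protocol and SAP*

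**What the plan says.** The amount of the dose is the same wherever it appears: 20 million viable cells. Section 3.2 adds a tolerance of 10% either way. The figures that should produce that amount are in four places.

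- **Concentration.** In Appendix C, for the active product, "dendritic cells will be concentrated down at $40 \times 10^6$ cells/mL in infusion media". For the placebo, "elutriated monocytes will be concentrated down at $40 \times 10^6$ cells/mL in infusion media". The administration paragraphs for the seven peptides in section 13 repeat 40 million cells/mL for the active product. In each case the next step is preparation in syringes.
- **Section 3.2.** For both groups the product is "administered intradermally in two sites on the forearm with a maximum volume of 0.5 mL per injection". The release standards include "flow cytometric verification of DC validation markers, viability" of at least 60%.
- **Appendix C, stability and storage.** The fixed dose of 20 million "viable cells/ in 0.25mL or 0.5mL will be administered immediately upon" receipt in the clinic.
- **Appendix D, report card.** The line "Total Injection Volume" is pre-printed as 0.5 x 2 = 1.0 mL, beside a dose line giving a total of 20 million viable cells. The only volume shown for each of the two sites is 0.5 mL.

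**The concern.** Concentration times volume should return the dose. With one concentration and one dose, only one total volume can be right, yet the documents give or allow 0.25, 0.5 and 1.0 mL. The concentration is also expressed in cells and the dose in viable cells, and nothing links the two.

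Section 3.2 describes this as the first use of the multi-epitope vaccine in humans, and section 3.3 allows no dose modification. The lead-in safety assessment and the randomised comparison both take the cell dose as known. Under section 6.1 a report card is obtained for each vaccination and its information is also entered in the medical record. If the card's volume and the product specification disagree, the record cannot show which cell dose a patient received.

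**Working it through.** **Inputs**

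| Quantity | Value | Source |
|---|---|---|
| Final concentration, both products | 40 million cells/mL | Appendix C; section 13 for the active product |
| Dose | 20 million viable cells | Section 3.2, Appendices C and D |
| Tolerance | 10% either way, so 18 to 22 million | Section 3.2 |
| Sites and maximum volume | 2 sites, at most 0.5 mL each | Section 3.2 |
| Minimum viability at release | 60% | Section 3.2 |
| Volume of one dose | 0.25 mL or 0.5 mL | Appendix C |
| Total volume on the card | 0.5 x 2 = 1.0 mL | Appendix D |

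Formulas: cells = concentration x total volume; viable cells = cells x viability, if the concentration counts total cells.

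**Step 1: which volume reproduces 20 million.** 40 x 0.5 = 20 million. A total of 0.5 mL reproduces the stated dose if the concentration counts viable cells, or if viability is 100%.

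**Step 2: the report card.** 40 x 1.0 = 40 million, which is twice the stated dose. The card implies a concentration of 20 / 1.0 = 20 million/mL.

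Could viability close the gap? If 40 million/mL counts total cells:

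- at 100% viability, 1.0 mL holds 40 million viable cells, 18 million above the upper limit of 22 million;
- at 60% viability, it holds 40 x 0.6 = 24 million, 2 million above the limit;
- to fall within 18 to 22 million, viability would have to be 18/40 = 45% to 22/40 = 55%, below the 60% release limit.

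So no releasable product at the stated concentration fits the card.

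**Step 3: Appendix C.** Cells at 40 million/mL:

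| Volume in Appendix C | Read as the total | Read as per site, two sites |
|---|---|---|
| 0.25 mL | 10 million | 20 million |
| 0.5 mL | 20 million | 40 million |

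Neither column gives 20 million in both rows. A mixed reading does (two sites of 0.25 mL, or one injection of 0.5 mL), but a single injection departs from the two sites in section 3.2.

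**Step 4: total or viable cells.** Assume that the concentration counts total cells and that volume is not adjusted for viability. The documents state neither. A total of 0.5 mL then holds 20 x 0.6 = 12 million to 20 x 1.0 = 20 million viable cells. It reaches 18 million only at 18/20 = 90% viability or more.

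If volume is instead adjusted for viability, 20 million viable cells need 20/(40 x 1.0) = 0.50 mL at 100% viability and 20/(40 x 0.6) = 0.83 mL at 60%. Both fit within two injections of at most 0.5 mL, but neither is the card's fixed 1.0 mL.

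**The case against.** The best defence is that the dose never varies: every passage gives 20 million viable cells. The product is made under protocol-specific instructions and standard operating procedures, is tested for cell content, concentration and viability before release, and reaches the clinic in prepared syringes. Nothing shows clinic staff deriving a dose from concentration and volume. A dilution step in procedures that we cannot see could make the card correct. This stands as a limit on the consequence: a dosing error is not shown. It does not make the protocol's own figures agree, because no dilution is stated in it.

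Four stronger readings are tempting and are not supported.

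- **A four-fold range of doses, 10 to 40 million.** The 10 million figure needs 0.25 mL to be the total. Read per site at two sites, it gives 20 million.
- **Section 3.2 is itself in conflict.** Its 0.5 mL is a maximum per injection, and step 4 shows that 20 million viable cells can be given within it.
- **Low viability makes matters worse.** For the 1.0 mL total it shrinks the excess over the upper limit, from 18 million to 2 million. It lowers the viable count at a 0.5 mL total, but only under the assumptions in step 4.
- **The arm comparison is blurred.** The same concentration, dose, volumes and card apply to both arms, and no effect on the endpoint is shown.

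**Conclusion.** The concern holds for the report card against the stated concentration: 1.0 mL at 40 million cells/mL is 40 million cells, against a dose of 20 million viable cells. This two-fold discrepancy survives both readings of the concentration, since the viability needed to remove it (45% to 55%) lies below the release limit. It rests on one assumption, that no dilution follows the concentration step, which is how the documents read.

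Two lesser gaps accompany it. Appendix C does not say whether its volumes are per site or totals, and the concentration is not identified as total or viable cells. The requirement of 90% viability at a 0.5 mL total depends on the further assumptions in step 4 and should be read as conditional.

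The point concerns a dose-defining figure and what the record can show about it. Type I error, power and sample size are not involved. Nothing here says which of the figures is right.

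**What to change.** Reconcile section 13, Appendix C and the report card with the dose in section 3.2, so that the following multiply out to one stated dose:

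- the concentration, identified as total or viable cells;
- the volume per site and the number of sites;
- the total volume, and whether it is adjusted for viability.

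If a dilution step exists in the manufacturing procedures, state it in Appendix C. Have the report card record the volume actually given at each site in place of a single pre-printed figure. The sponsor must decide which figures stand.

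The cost is a wording amendment and a revised card, with no new procedure. For doses already given, the manufacturing and release records, where they hold cell count, viability and volume, could be checked against the cards.

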#### 15.4 APPENDIX D: VACCINE BRANCH VACCINE REPORT CARD (VRC)

**Date of Administration (Day 1)** \_\_\_\_\_  
**Investigational Drug Dose #**  1  2  3  4  5  6 [a total of  $20 \times 10^6$  viable cells]

**Total Injection Volume**   $0.5 \times 2 = 1.0$  (ml)

[figure not shown]
**NOTES:**

1. For dose #1, vital signs should be documented pre-dose and 15, 30, 45 and 60 min after investigational drug administration. For all subsequent doses, vital signs should be documented pre-dose and 15 minutes after vaccine administration.
2. Investigational product labels must be placed on a progress note and sent to the Health Information Management Department (HIMD) to be scanned into CRIS.

Site	Injection Site	Injection Volume	ID Wheal	Today Day 1	Day 2	Day 3	Day 4	Day 5	Date Resolved
#1	Forearm  Left  Right	 0.5 mL	 Present  Absent	 0  1  2  3	 0  1  2  3	 0  1  2  3	 0  1  2  3	 0  1  2  3	
#2		 0.5 mL	 Present  Absent	 0  1  2  3	 0  1  2  3	 0  1  2  3	 0  1  2  3	 0  1  2  3	

- Use back of this page if reaction lasts more than 5 days or need more space to describe the symptoms.

Right       Left

--

Administered by (RN printed name & signature): \_\_\_\_\_

ISR reported by (patient or on behalf of the patient): \_\_\_\_\_

*Instructions to team: 1) Request that patient submits VRC via mail or at next visit 2) Keep a hard copy in the study chart, if available 3) Document findings in CRIS using free text NoteCetera VRC template.*

## **15.5 APPENDIX E: ANTI-TARP ANTIBODY AND CELLULAR RESPONSES**

The majority of the testing on this study will be done in the NIH Clinical Center clinical laboratory following their guidelines for blood collection and tube type. The appropriate tube for uncommon laboratory tests and immunologic research specimens and where they should be sent are as follows:

### **Quantitative Anti-TARP Antibody Testing: Weeks 3, 12, 18, 24, 36, 48, 60, 72, 84 and 96**

**Purpose:** To determine the immunogenicity of autologous multi-epitope TARP dendritic cell vaccination as measured by a 3-fold increase in anti-TARP antibody concentration (measured as mcg/mL) or a 4-fold increase in antibody dilution titers over baseline.

**Specimen Processing:** 1 10mL Red Top Clot activator

Specimens will be processed at the Clinical Support Laboratory Leidos Biomedical Research. Serum will be aliquoted into vials and cryopreserved until ready for interrogation in batched specimen assays.

### **TARP-Specific Cellular Response: Weeks 3, 12, 18, 24, 48, 60, 72, 84 and 96 CFSE**

**Proliferation, ICS, ELISPOT (IFN- $\gamma$ , Granzyme B, Perforin) & Tetramer Assays:**

6 10mL Green Top Heparinized Tubes (60 mL total)

Send via Frederick Courier to NCI Frederick Clinical Support Laboratory for specimen processing and freezing.

**Note:** PBMCs collected via apheresis that have completed monocyte elutriation processing by DTM and been subsequently cryopreserved by NCI Frederick, will be used for Week 0 cellular response assays.

Assays will be performed by the flow cytometry unit in the laboratory of [name].

The Clinical Support Laboratory, Leidos Biomedical Research, processes and cryopreserves samples in support of IRB-approved, NCI clinical trials. The laboratory is located in a controlled access building and laboratory doors are kept locked at all times. Upon specimen receipt, each sample is assigned a unique, sequential laboratory accession ID number. All products generated by the laboratory that will be stored either in the laboratory freezers or at a central repository facility are identified by this accession ID. An electronic database is used to store information related to patient samples processed by the laboratory. Vial labels do not contain any personal identifier information. Samples are stored inventoried in locked laboratory freezers and are routinely transferred to the NCI-Frederick repository facilities for long-term storage. These facilities are operated subcontract to Leidos Biomedical Research. Access to stored clinical samples is restricted. Investigators establish sample collections under "Source Codes" and the investigator is responsible for the collections, typically the protocol Principal Investigator who has access to the collection. Blood and tissue specimens collected in the course of this research project may be banked and used in the future to investigate new scientific questions related to this study. The PI will record any loss or unanticipated destruction of samples as a deviation. Reports will be made per the requirements of section **7.2**.

## 15.6 APPENDIX F: EXPLORATORY CORRELATIVE STUDIES

Multiparameter Flow Cytometric Analysis of Circulating Tumor Cells (CTC) and Other Immune Cell Subsets: [name], DTB

Analysis will be performed by the laboratory of [name]. CTC cells and other immune cell subsets will be identified by mulitparameter flow cytometry. The order of priority for immune subset analysis is T, B, NK, NKT, MDSC and dendritic cells. A total of 30 mL of blood in lavender top tubes will be collected.

### CTC Analysis:

**Weeks 3 (baseline), 12 (s/p 3 doses of vaccine), 18 (s/p 5 doses of vaccine), 24, 48, 72 and 96**  
Highly multiparametric flow cytometry with on-line physical isolation employing a Miltenyi Biotec platform will be utilized for interrogation of CTC with customized parameters including tumor markers and hematopoietic markers.

### Immune Cell Subset Analysis:

**Weeks 3, 12, 18, 24, 48, 72 and 96**

Multiparametric flow cytometry using a Miltenyi Quant flow cytometer. The order of priority for immune subset analysis is T, B, NI, NKT, MDSC and dendritic cells.

## 15.7 APPENDIX G: GUIDELINES AND WORKSHEET FOR CALCULATIONS OF PSADT

Study Number: \_\_\_\_\_

### Pre-NIH and On Study PSADT Calculation:

- PSADT will be calculated using the Memorial Sloan-Kettering Cancer Center cancer information prostate nomogram for PSA doubling time found at:  
<http://nomograms.mskcc.org/Prostate/PsaDoublingTime.aspx>.
- Minimum requirements for PSADT include  $\geq 3$  PSA measurements over  $\geq 3$  months.
- The interval between PSA measurements must be  $\geq 4$  weeks.
- For patients receiving 5-alpha reductase inhibitors (5ARI) e.g. finasteride or dutasteride, only PSA values obtained after at least 3 months on therapy may be used to calculate PSADT.
- PSA values used in the calculation of PSADT must have been performed by the same laboratory, when possible.
- All PSA values used in the calculation should be  $\geq 0.2$  ng/mL and follow a rising trend although all values need not be consecutively rising.
- All values obtained over a maximum period of 12 months prior to enrollment will be utilized to calculate the patient's Pre-NIH PSADT.

Date Range of PSA Values (should not exceed 24 months): \_\_\_\_\_

Cumulative Total Months of PSA Values (should not exceed 24 months): \_\_\_\_\_

Receiving Flomax:  YES  NO      Start Date: \_\_\_\_\_ On at least 3 Months:  YES  NO

Receiving 5ARI:  YES  NO      Start Date: \_\_\_\_\_ On at least 3 Months:  YES  NO

DATE	PSA ng/mL	TESTOSTERONE ng/dL	PSADT

Record PSA values with a maximum of 2 digits after the decimal point.

NIH PSA values in blue.

Calculated Pre-Enrollment/Baseline PSADT (in months)/ Slope Log PSA: \_\_\_\_\_

Value is  $> 3.0$  Months and  $\leq 15$  Months:  YES- Eligible

NO- Ineligible for Study

**Study Number:** \_\_\_\_\_

**Calculated Pre-Enrollment/Baseline PSADT (in months):/ Slope Log PSA:\_\_\_\_\_**

**PSADT/Slope Log PSA will be calculated at Weeks 15, 18, 24, 36, 48, 60, 72, 84 & 96. Calculate using PSAs from both the entire study period and the prior 6 months.**

Date	Study Week #	PSA ng/mL	Testosterone (ng/dL)	PSADT
	0			Value NOT used in calculations
	3			PSADT is not calculated at this point
	6			PSADT is not calculated at this point
	9			PSADT is not calculated at this point
	12			PSADT is not calculated at this point
	15			
	18			
	24			
	36			
	48			
	60			
	72			
	84			
	96			

**Record PSA values with a maximum of 2 digits after the decimal point.**

PSADT Calculated for Statistical Analysis			
Analysis Window	Study Wk PSA Values Included	PSADT/Slope Log	Percent Change PSADT
Pre-NIH	Time of Entry		
Week 3 to Week 15	Wks 3, 6, 9, 12, 15		
Week 3 to Week 24	Wks 3, 6, 9, 12, 15, 18, 24		
Week 3 to Week 48	Wks 3, 6, 9, 12, 15, 18, 24, 36, 48		
Week 24 to Week 48	Wks 24, 36, 48		
Week 48 to Week 72	Wks 48, 60, 72		
Week 48 to Week 96	Wks 48, 60, 84, 72, 96
